Thus, CSA represents an effective therapy for inducing remission of nephrotic syndrome in patients with IMN. It leads to remission of proteinuria in the majority of nephrotic patients with IMN but with less potential serious toxicity compared to the use of cytotoxic/alkylating agents. There is also more experience with CSA (versus other CNI) in the US and Canada and for these reasons it has been chosen as the comparator arm for our study.

Patients with IMN that do progress do so over years and follow-up in RCTs with CNI therapy have not been of sufficient duration to illustrate improvements in renal survival. However there is well documented recent data that indicates that both complete and partial remission in proteinuria is associated with improved renal survival. Complete remission was associated with a 100% 10-year survival and partial remission (defined as more than a 50% decrease from baseline and attaining a urine protein level of <3.5 g per day) was associated with a 90% 10 year renal survival compared to 50% kidney survival in those that fail to remit. In addition, in this same study PR as measured by slope of CCR, resulted in a slowing of progression rate of >80 % compared to non-remitters.⁴²

Toxicity of cyclosporine

Cyclosporine is a potent immunosuppressive agent and is associated with significant risk of both short and long-term toxicity. In the majority of cases these adverse effects are associated with both total daily dose and total exposure. Precise incidences of these toxicities are hard to ascertain from the literature given the rarity of studies where these agents are used as monotherapy and their use for a limited duration as proposed in this trial. There is however undoubtedly an acute effect on filtration function and delayed effects on renal vasculature that have been well documented and a recent review summarized both short and long-term toxicities associated with this agent.⁵⁸ Hypertension, overgrowth of body hair and gingiva hyperplasia, mild tremor, infections, elevated bilirubin levels and mild nausea represent the most frequently observed short-term adverse effects related to CSA.⁵⁸ These are seen in up to 20 to 30% of the treated population but are usually tolerated and/or treatable with additional agents (such as additional anti-hypertension drugs) or by dose reduction.⁴⁸

Cyclophosphamide (CYC)

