CR or PR (defined as per table 1) at 24 months after randomization will be the primary endpoint. This will be assessed in an intention to treat (ITT) analysis.

Secondary endpoints

1. Relapse state at month 24 after randomization (Urine Protein (UP) $> 3.5\text{ g}/24\text{h}$ after earlier CR or PR)
2. Anti-PLA2R levels
3. Quality of life as measured by modified KDQOL
4. Adverse events

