5. ESRD
6. CR or PR, and CR alone at 6, 12, 18, and 24 months after randomization
7. Time to CR or PR
8. Effect of treatment on renal function, as assessed by slope of creatinine clearance from baseline to 24 months.

Table 1. Definition of remission status

Remission status	Proteinuria (UP g/24 hours) after treatment
Complete remission (CR)	UP \leq 0.3 g/24h and serum albumin \geq 3.5g/dl
Partial remission (PR)	Reduction in baseline UP of \geq 50% plus final UP \leq 3.5 g/24h but $>$ 0.3 g/24h
Non-response (NR)	Reduction in baseline UP of $<$ 25% (includes increase in UP)
Relapse	Development of nephrotic range proteinuria following CR or PR, i.e. $>$ 3.5g/24h

Patient recruitment

The study population will be comprised of individuals with biopsy-proven idiopathic MN. Total study size will be 126 patients, enrolled among up to 25 participating sites. Potential candidates for the study will be identified by the investigators using existing databases and clinical trial networks. The P.I. or the study coordinator will contact these potential candidates and if the preliminary interview indicates their willingness to participate, a consent form will be reviewed with the patient. If a potential candidate remains interested, the consent form will be signed, and the patient enrolled in the study. The institutional review board at each participating site will approve the recruitment process and consent forms. The Mayo Nephrology Collaborative Group (MNCG) will post information on its web site describing the study and identifying local contacts at the collaborating centers. Each site involved may have their own methods of informing and recruiting potentially eligible patients but in all cases will have IRB approval before embarking on this process. Each site will be expected to randomize approximately 6-10 patients over the recruitment period. If, based on site estimates of the IMN population that would be eligible for this study, we enroll approximately 30% of the annual population in a single year our recruitment will be complete. We have assembled a consortium for this trial with a population that well exceeds the enrollment needs based upon the multi-year enrollment plan for this trial.

Recruitment strategy

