- Idiopathic MN diagnosed by renal biopsy (original biopsy needs to include light, immunofluorescence and electron microscopy); pathology report must be adjudicated by a study PI ([name] or [name], or documented delegate) prior to randomization.
- Age 18-80 years inclusive
- If female, must be post-menopausal, surgically sterile or practicing a medically approved method of contraception (with exception of no birth-control pill given the potential for increased risk of thromboembolism in the nephrotic setting).
- Patient must be off prednisone or mycophenolate mofetil for >1 month and alkylating agents for >6 months. The rationale is to minimize the potential confounding effect of delayed benefits from previous immunosuppressive agents and to reduce the risk of too much immunosuppression from the combined previous drug exposure plus trial drug exposure, e.g. infections.
- Treatment with an ACEi and/or ARB, for ≥3 months prior to randomization and adequate blood pressure control (target BP is <130/80 mm Hg in >75% of the readings, but subjects with BP <140/80 mmHg in >75% of the readings will be eligible).

OR

If patient is intolerant to even a very low dose of either ACEi or ARB therapy, approval for participation in the trial has been obtained from the study PI(s) prior to randomization.

Patients with documented evidence of ≥3 months treatment with maximal angiotensin II blockade, on an HMG-CoA reductase inhibitor, and BP control (BP <140/80 mm Hg in >75% of the readings) who remain with proteinuria ≥5g/24h and meet the other eligibility criteria (as confirmed at the Time 0 visit by the central lab results) may enter the treatment phase of the study and be randomized to RTX/CSA without the need of the run-in/conservative phase of the study. However, in addition these patients must have a documented <50% reduction in proteinuria compared to previous 24 hr proteinuria or Uprot/Ucrea ratio estimates during this period of ACEi and/or ARB treatment otherwise they must fulfill the run-in requirement.

- (Please refer to manual of operation for clarification of tests mandated for patients who are randomized without the run-in period)

- Proteinuria $\geq 5\text{g}/24\text{h}$ using the average from two 24-hour urine collections collected within 14 days of each other despite Ang II blockade for ≥ 3 months as described above.

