3. Patients who discontinue Cyclosporine for ≥ 4 weeks will not be restarted on study drug, but will continue with full visit follow-ups until month 24 as scheduled. The therapeutic/management plan will be solely at the discretion of the managing nephrologist.

Laboratory testing

In order to contain costs all clinical tests will be carried out locally at the recruiting centers. However, at critical time points: Time 0, and 6, 12, 18, and 24 months from start of treatment, recruiting centers will ship to Mayo Clinic, Rochester, Minnesota, 2 blood samples and 2 urine samples (aliquots obtained from two 24h urine collections) for determination of serum creatinines, serum albumins and urinary protein/creatinine ratios. Blood and urine kits will be provided by Mayo Clinic, Rochester, Minnesota, for these

samples along with shipping costs (see Lab Manual). The Central Lab results (Mayo Clinic, Rochester, MN) will be used for statistical purposes since this will ensure a standard methodology is applied to the critical (for the trial analysis) laboratory assessments. By measuring the volume of the 24-hour urine collection we will also be able to calculate both clearance and the 24-hour urine protein from the aliquot. Proteinuria results at Time 0, 6, 12, 18 and 24 months will be taken as the mean of two 24-hour urine collections done back to back (within 14 days of each other), and the mean of these 2 collections will be used to determine CR, PR, or NR.

In order to control for the possibility of under collection or over collection of urine, a maximum 20% variation in total 24h urine creatinine (mg/specimen) will be allowed between the two urine collections required at Time 0, 6 months, 12 months, 18 months, and 24 months. A difference of greater than 20% will necessitate a third urine collection (also to be sent to the central lab), with the values from one of the two previous collections being discarded. We will use the subject's weight to approximate the expected total urine creatinine (mg/kg) to determine which of the previous collections is closest to the truth and which should be discarded. It is anticipated that a 3rd urine collection will be needed in <10% of cases. Proteinuria will be calculated as the mean of these two 24-hour urine collections.

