Sample size estimation: The primary study goal is to compare the long-term efficacy of RTX (given at baseline and repeated at 6 months) with CSA (12 months treatment + 2 months taper) using proteinuria response 24 months after randomization. Proteinuria positive response will be defined as attaining and maintaining CR or PR at 24 months after randomization. We propose to establish that the RTX treatment is non-inferior to the CSA. RTX will be considered non-inferior to CSA if the response rate of the RTX arm is at most 15% worse than that of CSA arm. In addition we will compare the quality of life (QOL) and adverse event (AE) profile over the course of the treatment period. The preliminary data has indicated that CSA is effective in inducing a CR/PR of proteinuria in between 60 and 75% of MN cases.^{48, 51} However, nephrotic syndrome (NS) relapses may be as high as 50% once CSA is discontinued.⁸⁵ Thus, we estimate a CR/PR rate in patients treated with CSA of 30-50% at 24 months after randomization.⁸⁵ Similar remission and relapse rates with the use of Tacrolimus (another calcineurin inhibitor) have been reported by Praga et al.⁵⁶ In this latter study, almost half of the MN patients had a relapse of the nephrotic syndrome after tacrolimus was discontinued.⁵⁶ On the other hand, based on the long term follow up on the 35 patients treated with RTX from our 2 studies, we estimate the relapse rate to be <10% at 24 months.^{71, 75} We observed a CR/PR rate at 12 months, very similar to the rate for calcineurin inhibitors i.e. 60%, and in our second study completed recently, we observed an 80% CR/PR rate at 24 months, implying that RTX had a ~20% failure rate with 95% (CI 6% to 44%). To be conservative for the sample size estimation, we considered a maintained CR/PR rate at the low end of our previous experience, 55% CR/PR for RTX at 24 months and at the high end of our experience with CSA (CNI therapy) CR/PR for CSA of 45%. We propose a non-inferiority trial with non-inferiority margin $\delta = 15\%$, with the null hypothesis of $\pi_{RTX} - \pi_{cyclosporine} < \delta$, where π_{RTX} and $\pi_{cyclosporine}$ are the proportions of patients with CR/PR at 24 months in treatment arms of RTX and CSA, respectively. Under these assumptions, and a one sided alpha of 0.025, enrollment of 63 evaluable patients per study arm is required to achieve 80% power to show that the RTX is not inferior. For the intent to treat (ITT) analysis we will consider all patients lost to follow up to be non-responders so no correction to the sample size is needed for dropouts. With 63 patients per arm we will have 80% power to detect moderate differences of .6 standard deviations for continuous measures or around .25 for proportions for the comparisons of the QOL and AEs.

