
Statistical and Analytical Plan: All demographics and entry laboratory data will be summarized by treatment group. Frequency distributions will be used to describe categorical values and basic summary statistics (mean, standard deviation, median, and inter-quartile range) will be used to describe continuous values. To provide more reliable estimates and minimize the “regression to the mean effect” duplicate urine measurements obtained at baseline (Time 0), 6, 12, 18 and 24 months will be averaged. The chi-square test and logistic regression will also be used to compare the percent of patients with remission at 6, 12, 18, and 24 months adjusting for treatment center and the baseline

proteinuria (UP<8g/24h vs >=8g/24h). Odds ratios and associated 95% confidence intervals will be estimated. The formal test for the primary endpoint will be based on the significance of the treatment group factor in the logistic regression model for UP failure at month 24. The Wilcoxon rank-sum test and ordinal logistic regression will be used to compare the ordered remission status outcome (1=CR, 2=PR, 3=NR) between treatment groups. Longitudinal methods for categorical outcomes (e.g. generalized estimating equation or GEE models) will be used to compare remission status profiles between treatment arms. Unless otherwise noted, all tests will be two-sided with alpha level 0.05.

For repeated measures such as urine protein, individual rates of change will be estimated using within-patient linear regression analyses (including data from all visits). Because of the non-linearity of the changes in proteinuria log transformation estimates will be used. Renal function readings will be censored at initiation of dialysis or renal transplant. Additionally, mixed effects models, assuming a random center effect, and a random slope of creatinine clearance and/or reciprocal of creatinine and intercept for each patient will be fit using data from all visits. These models allow comparison of the average slope between groups, while taking into account that each patient's slope may be based on a variable number of readings. Treatment group comparisons regarding quality-of-life scales will be done using repeated measures analyses and mixed effects models.

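### Table 1 leaves proteinuria of 0.3 g/24h or less with albumin below 3.5 g/dl outside both CR and PR, so a better urine result can literally miss the primary endpoint that a slightly worse one meets

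*Combined protocol and SAP*

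**What the plan says.** - **Primary endpoint:** "CR or PR (defined as per table 1) at 24 months after randomization will be the primary endpoint". The sample size section repeats the response rule: "Proteinuria positive response will be defined as attaining and maintaining CR or PR at 24 months after randomization".
- **Table 1, CR:** UP of at most 0.3 g/24h together with an albumin condition ("g/24h and serum albumin" of at least 3.5 g/dl).
- **Table 1, PR:** at least a 50% reduction from baseline, with final UP at most "3.5 g/24h but $>$ 0.3 g/24h". There is no albumin condition.
- **Table 1, NR:** a reduction of less than 25%.
- **Inclusion Criteria:** entry proteinuria of at least 5 g/24h, "using the average from two 24-hour urine collections collected within 14 days of each other".
- **Overall Research Design and Methods:** efficacy is judged by remission status, which is said to rest on proteinuria change.
- **Laboratory testing:** the averaged urine collections decide between CR, PR and NR. The same section sends central samples at Time 0 and months 6, 12, 18 and 24 "for determination of serum creatinines, serum albumins and urinary protein/creatinine ratios", so albumin is available at each of these visits.
- **Statistical and Analytical Plan:** the formal test is of the treatment factor "in the logistic regression model for UP failure at month 24". The intention-to-treat paragraph treats urine protein failure at month 24 as the primary endpoint. Neither place defines the term. The ordinal analysis codes CR as 1, PR as 2 and NR as 3.

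**The concern.** The two success categories do not meet. CR carries an albumin condition and PR does not, but PR stops at 0.3 g/24h. Someone who gets below that level and misses CR on albumin alone has no category to fall back to. The order of outcomes is then reversed at the threshold: less proteinuria scores worse than more, at the same albumin.

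This sits in the definition of the primary endpoint. It carries over to the secondary endpoint of CR or PR at months 6, 12, 18 and 24. Time to CR or PR is touched less, because a patient seen in the PR range at an earlier visit already has an event date. Only those who pass through that range between visits are affected.

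The plan also describes the outcome in two ways, by Table 1 with albumin and by urine protein alone. Two analysts could score this patient differently, and in an open-label trial that choice should be fixed before the data are seen.

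**Working it through.** **1. Apply Table 1 literally.** Inputs are the CR, PR and NR rows and the 5 g/24h entry minimum. Reduction = 1 − UP/baseline. The albumin values are chosen to fall on either side of the 3.5 g/dl limit.

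| Baseline UP (g) | UP (g) | Albumin (g/dl) | Reduction | Table 1 |
|---|---|---|---|---|
| 5 | 0.31 | 3.4 | 1 − 0.31/5 = 93.8% | PR |
| 5 | 0.30 | 3.4 | 1 − 0.30/5 = 94.0% | none of CR, PR, NR |
| 5 | 0.20 | 3.4 | 1 − 0.20/5 = 96.0% | none of CR, PR, NR |
| 5 | 0.30 | 3.5 | 94.0% | CR |
| 13 | 0.31 | 3.4 | 97.6% | PR |
| 13 | 0.30 | 3.4 | 97.7% | none of CR, PR, NR |

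Baselines of 8 and 11.9 g give the same pattern. Since 5 g is the lowest eligible baseline, 94% is the smallest reduction that an affected patient can have. No other section assigns this patient to a category.

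**2. Test the repair.** With the lower limit of 0.3 g removed from PR and CR taking precedence, every tested case with UP at or below 0.30 g and albumin 3.4 g/dl becomes PR. No other tested case changes.

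**3. Reproduce the planned sample size.** Inputs from the sample size section are RTX 55%, CSA 45%, margin 15 points, one-sided alpha 0.025 and power 80%.

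- n per arm = (1.960 + 0.842)² × (0.55×0.45 + 0.45×0.55) / (0.15 + 0.10)² = 7.85 × 0.495 / 0.0625 = 62.2, rounded up to 63. This matches the plan.
- At n = 63, SE = √(0.495/63) = 0.0886. Power = Φ(0.25/0.0886 − 1.960) = 80.5%.

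**4. Size of the effect.** One patient is 1/63 = 1.6 points of an arm's rate, against a 15-point margin. The number affected is not in the documents, so the counts below are assumptions.

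| Successes lost | Both arms | RTX only | CSA only |
|---|---|---|---|
| 1 | 80.6% | 75.1% | 85.2% |
| 2 | 80.7% | 69.0% | 89.1% |
| 3 | 80.9% | 62.5% | 92.2% |

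Equal losses leave power where it was (81.5% at five per arm). Unequal losses push it either way, depending on which arm has more such patients, and the documents do not settle that.

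**5. Ordinal code.** A fall from 10 to 6 g is a 40% reduction, and a fall from 10 to 4 g is a 60% reduction that ends above 3.5 g. Neither patient is in CR or PR, and neither meets NR at less than 25%, so the three-level outcome has no code for them. This is a separate gap. It does not affect the binary primary endpoint, where both are plainly failures.

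**The case against.** The strongest reply is that no sentence says an unclassified patient fails. The design section, the urine-only classification under Laboratory testing and the label urine protein failure all point to scoring on urine, and 0.2 g/24h is hard to call a urine protein failure. That stands in part. A reader might infer that the plan settles the matter as a failure, and the wording as a whole does not go that far. It does not remove the point, though: the primary endpoint is tied expressly to Table 1, and under Table 1 this patient is not a success. The competing wording is a further reason to fix the rule.

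A second reply is that the albumin condition is deliberate. It may well be, as a reason to withhold CR. It does not explain falling below PR, because PR has no albumin condition and accepts the same albumin at 0.31 g.

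Three stronger readings are tempting and are not supported.

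- **A loss of power against RTX.** Suppose a fraction of complete remitters have low albumin, with complete remission rates of 4/20 = 20% for RTX and 0.75 × 0.10 = 7.5% for CSA. Fractions of 5%, 10% and 20% then give power of 78.5%, 76.3% and 71.8%. The fraction is invented. The RTX rate is a 24-month figure from the four-dose pilot, and the CSA rate is a 26-week figure from a trial that added prednisone. The pilot at this trial's dose gives 2/14 at 12 months, or 5/14 with later conversions; at a 20% fraction these yield 76.0% or 58.8%. A common 20% remission rate in both arms yields 80.5% to 80.8%. It is also not stated whether the planned 55% and 45% count these patients as responders.
- **Misgrouping on renal survival.** The Cyclosporine background section cites a PR that is "defined as more than a 50% decrease from baseline and attaining a urine protein level of <3.5 g per day", with 90% ten-year renal survival against 50% without remission. That is a brief summary of one study. It does not define CR and it lists CR and PR as separate groups, so it cannot show which prognosis this patient has.
- **A contradiction with the month-6 treatment rules.** The Rituximab and Cyclosporine sections already give a route to a patient with at least a 25% reduction who is not in CR. No conflict is shown there.

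**Conclusion.** The point holds as a minor defect in the definition of the primary endpoint. On its literal terms Table 1 denies success to a patient with UP of 0.3 g/24h or less and albumin below 3.5 g/dl, after a reduction of at least 94%, while the same patient at 0.31 g succeeds. The reversal follows from Table 1 and the 5 g entry minimum, without further assumptions. It also conflicts with the plan's description of the endpoint as a urine measure.

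The effect on the result is undocumented and probably small: 1.6 points of an arm's rate per patient, in an unknown direction between arms. The sample size of 63 per arm stands, and no power loss can be claimed.

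**What to change.** For endpoint scoring only:

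1. In Table 1, define PR as at least a 50% reduction from baseline with UP of at most 3.5 g/24h, not meeting CR. This drops the lower limit of 0.3 g/24h. If the sponsor does intend these patients to be failures, Table 1 should say so and give the reason.
2. In the Statistical and Analytical Plan, state that UP failure at month 24 means neither CR nor PR under Table 1. Align the Laboratory testing wording, so that albumin is named where CR is decided.
3. As a separate clarification, define ordinal code 3 as neither CR nor PR, which also covers relapse.

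The cost is a few lines of text. No new data are needed, because albumin is already measured centrally at the endpoint visits, and the sample size does not change. No change to any treatment rule is proposed.
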